## **2.0 \* Identify the variables to be measured and how they will be statistically evaluated:**

Formal Analysis of our Primary Hypotheses: First, the two arms will be compared on all variables at baseline to determine if statistically significant differences are present. If differences are found on baseline measures, they will be examined as covariates in all statistical models of interest in exploratory analyses. Importantly, only the pre-specified covariates of baseline outcome variable, gender, and site will be included in the primary and secondary analyses. For comparing the

Mentoring Program to the Educational Activity group on pre-post change for our primary analysis, the baseline measure of QOL for youth with IBD along with the gender and site will be included as covariates in the primary analysis, regardless of the results of statistical tests for baseline group differences. The following repeated measures (RM) model, similar to an analysis of covariance (ANCOVA), will be employed,  $y_{it} = B_0 + B_1 \text{Time}_i + B_2 \text{Time}_i \times \text{Trti} + B_3 \text{Gender}_i + B_4 \text{Site}_i + e_{it}$ , where implicitly it is assumed that there is no main effect of  $\text{Trti}$ ,  $y_{it}$  is the QOL for youth  $i$  at time  $t$ ,  $\text{time}_i$  is coded as 0 for the pretest and 1 for the post-intervention measure, and the primary effect of interest is  $B_2$ , which corresponds to the difference between the groups on change in youth's QOL. In this RM model, the baseline measure of QOL for youth is constrained to have equal means across groups by assuming there is no main effect for  $\text{trti}$ . This constraint yields a statistical test for  $B_2$  analogous to the test of a treatment group main effect in an ANCOVA, controlling for baseline QOL. The main advantage of the RM model is that it can be estimated in SAS PROC MIXED using maximum likelihood estimation by treating  $\text{Time}_i$  as a repeated measures factor with two levels, whereas an ANCOVA model would require listwise deletion to account for missing data.

Formal Analysis of our Secondary Hypotheses: The same approach and statistical models employed for our primary hypotheses will be used for our secondary hypotheses within Hypotheses 1, 2, and 3. The main difference between the precise models used will be (a) the specific outcome variable and (b) the time point, post-intervention or 6 month follow-up, employed to form the change score for the hypothesis of interest.

Formal Analysis of our Exploratory Hypotheses: For Hypothesis 1, the RM model specified in our primary hypothesis will be employed, with the exception that the only effect in the model will be a main effect of  $\text{Time}$ , and the model will only be employed within the Mentoring Program group, since mentors are only available within this study arm. For Hypothesis 2 contained within our exploratory aim, we will employ a longitudinal mediation model with multiple mediators. Specifically, the figure illustrates the model of interest for examining the indirect effects of Mentoring Program compared to Educational Activity on QOL at the 6 month follow-up via the pathway of social support measured at the intermediate time point between baseline and post-intervention. The advantages of longitudinal data to examine mediation models have been well-documented in the methodological literature, yielding a unique opportunity for us to test these pathways over time within an RCT. We will use Mplus 7.31 and its state-of-the-art bootstrapping procedures to statistically test parent and child self-efficacy, illness uncertainty, coping and social support as mediators for the outcome of interest both individually and simultaneously, the latter being useful for determining if a particular mechanism accounts for substantially more variance in the treatment effect. We will follow the guidelines specified for testing longitudinal mediation within Cole and Maxwell and MacKinnon. We will allow for the possibility of a residual direct effect within our models. This same general approach will be used to examine all our mediators. For Hypothesis 3, sex will be examined as a moderator of the treatment effect by examining the three-way interaction between sex, time, and treatment group, while also including all two-way effects and the main effect associated with sex, into the statistical model employed for the primary hypothesis.

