### 2.0 If applicable, provide a statistical sample size justification stated in terms of study power or confidence interval width.

Our power analysis is based on our primary hypothesis that the Mentoring Program will provide a significantly greater increase in QOL compared to the Educational Activity group from baseline to post-treatment. We use a Type I error rate of .05 to test this primary hypothesis. For examining statistical power, we assume an independent samples t-test is used to test this hypothesis with a minimum of 80% power to obtain a sufficient per group sample size ( $n$ ), which is assumed equal across groups. Consequently, the standardized mean difference is the effect size required to obtain power and sample size. Our primary analysis also allows for the inclusion of site, gender and the baseline measure of the outcome as covariates, which will allow for an  $n$  equal to or smaller than that reported here for the same level of statistical power.

The results of our pilot study are used to estimate effect size for our power analysis. We found a standardized mean difference of .52 on the QOL total scale when examining group differences in pre-post change. We found effect sizes of .52 and 1.08 on the functional disability score and on the QOL social scale respectively, thus generally illustrating that we should expect effect sizes in the medium to large range for the current R01. Our sample size of n=100 per group (mentoring vs. comparison) would provide 94% power for a medium effect size of d=.5 and more than 99% power to detect a large effect size of d=.8. Even with 20% attrition, we would still have 88% power to detect a medium effect size and over 99% power to detect a large effect size. Thus, our sample size of n=100 is sufficient for detecting treatment effects that we would expect.

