## Recruitment and Retention Tools

### 1.0 \* Describe local recruitment strategies/plans for potential study subjects and where recruitment will be done:

Youth participants: After diagnosis is confirmed, patients at two sites (NCH, CCHMC) participate in a "teaching visit" or educational group visit to learn about the disease and the clinic. On-going research at the clinic is also discussed, so we will approach patients about enrolling in the project at this time. Other potential youth participants will be approached via recruitment letter, brochure, phone call and/or clinic visit.

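### The primary model holds gender and site effects constant over time, so these covariates adjust the change comparison only partly; precision can be lost, and a small dropout bias is possible

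*Combined protocol and SAP*

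**What the plan says.** Methods 2.0, under the formal analysis of the primary hypotheses, states that "the baseline measure of QOL for youth with IBD along with the gender and site will be included as covariates in the primary analysis", and that "only the pre-specified covariates of baseline outcome variable, gender, and site will be included in the primary and secondary analyses". The model given there has an intercept, Time (0 at baseline, 1 post-intervention), Time × Trt, Gender, Site and a residual. Treatment has no main effect, so the arms share a baseline mean. The target is B2, the Time × Trt coefficient, which "corresponds to the difference between the groups on change in youth's QOL". Time is interacted only with treatment. The covariance structure of the two measurements is not named.

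The model is called "similar to an analysis of covariance (ANCOVA"), and the test of B2 is described as "analogous to the test of a treatment group main effect in an ANCOVA, controlling for baseline QOL", a property that the plan attributes to the equal-baseline constraint.

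The next paragraphs of Methods 2.0 carry the same model to the secondary hypotheses. Only the exploratory sex-moderator model adds all two-way effects, so sex × time appears there but not in the primary model.

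Sample Size Information 2.0 bases power on an unadjusted two-sample t-test and adds: "Our primary analysis also allows for the inclusion of site, gender and the baseline measure of the outcome as covariates". It expects the covariates to leave the required sample size the same or smaller.

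**The concern.** Two covariates are pre-specified for a comparison of change, yet the equation lets neither of them affect change. If sites or sexes differ in how QOL moves over the year, that difference goes into the residual of the primary test. Because the secondary between-arm analyses reuse the model, they inherit the restriction.

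Two things are at stake: the precision of B2, and its robustness when dropout differs by site and arm. The second matters because the plan chose this model over a conventional ANCOVA for its handling of missing data. Site-specific dropout in one arm is conceivable, since mentors are matched partly on where they live.

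One possible source of site differences is recruitment. Recruitment and Retention Tools 1.0 says: "After diagnosis is confirmed, patients at two sites (NCH, CCHMC) participate in a" teaching visit, where the study can be offered. Those sites may therefore enrol more newly diagnosed youth. That QOL would move differently in such youth is an inference; the documents do not say so.

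**Working it through.** **1. The plan's own power.** Inputs from Sample Size Information 2.0: α = .05, d = .5, 100 per group, 20% attrition (80 per group). The noncentrality is .5√(100/2) = 3.54 and .5√(80/2) = 3.16. A two-sided t-test then has power 94.0% and 88.2%. The stated 94% and 88% reproduce.

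**2. What the written model implies.** Subtracting the two time points gives E[y₁ − y₀] = B1 + B2·Trt, so gender and site cancel. Let a covariate's true effects be γ₀ at baseline and γ₁ at follow-up, and let β be the slope of follow-up on baseline. An ANCOVA of follow-up on baseline, arm, gender and site estimates γ₁ − βγ₀ freely. The written model forces γ₀ = γ₁ = B3, which gives (1 − β)B3. It is thus an ANCOVA with a restricted covariate coefficient. The two agree when γ₀ = γ₁. Otherwise, the repeated-measures equivalent of the adjusted ANCOVA needs the covariate × Time terms.

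**3. Large-sample cost.** Assume a 50/50 covariate, equal variances, unstructured covariance, correlation ρ, and a difference D in mean change between covariate levels (within-cell SD units). The variance of B2 as written, relative to the model with × Time terms, is

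[1 + D²/(8(1 − ρ))] / [1 + D²/16].

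For ρ = .6 and D = .5: (1 + .25/3.2)/(1 + .25/16) = 1.0781/1.0156 = 1.062, or 3.0% in SD. The documents give neither ρ nor D, so the range is shown:

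| D | ρ = .3 | ρ = .5 | ρ = .6 | ρ = .7 |
|---|---|---|---|---|
| 0 | 1.000 | 1.000 | 1.000 | 1.000 |
| .2 | 1.005 | 1.007 | 1.010 | 1.014 |
| .5 | 1.029 | 1.046 | 1.062 | 1.087 |
| .8 | 1.071 | 1.115 | 1.154 | 1.218 |

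**4. Simulation at the trial's size.** Taken from the documents: 200 youth, 20% attrition, four sites (the lead site plus three relying sites). Assumed: ρ = .6, site sizes 70/45/45/40, a gender effect on change of .2 SD in the non-zero settings, simple randomization. Sampling SD of B2 in two sets of runs (the first with 4,000 trials per setting):

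| Site difference in change | As written | With × Time terms | Ratio |
|---|---|---|---|
| 0 | .1278; .131 | .1298; .132 | .985; .992 |
| .3 SD | .1283 | .1283 | 1.000 |
| .5 SD | .1320; .1325 | .1289; .1293 | 1.024; 1.025 |
| .8 SD | .1378; .140 | .1275; .127 | 1.081; 1.10 |

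The second set was also about equal at .2–.3 SD. The sampling SD is used rather than the average maximum-likelihood standard error, because the latter runs low as parameters are added. At .3 SD the average standard errors suggest a 1.8% gain (.1274/.1252) that the spread of the estimates does not show.

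**5. Power.** Reading d = .5 on the change-score scale, the effect is .5√(2(1 − .6)) = .447 SD, and power is approximately Φ(.447/SD − 1.96). With the second set of SDs, as written against with × Time terms: 93% and 92% at 0; 92% and 93% at .5 SD; 89% and 94% at .8 SD. None falls below 88%. More generally, the written model's variance relative to a t-test on change is (1 + ρ)/(2(1 + D²/16)), which is below 1.

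**6. Balance within site.** The documents do not say whether randomization is stratified by site. If arms are balanced within site, the true spread differs less: .6%, .5% and 2.3% at .3, .5 and .8 SD. The loss then appears mainly as a relatively conservative standard error. At .5 SD the average standard error divided by the true spread is .1295/.1294 = 1.00 as written and .1240/.1287 = .96 with the × Time terms.

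**7. Dropout differing by site and arm.** Assume 40% mentoring-arm dropout at one site, 10% at the others, and 20% in the comparison arm. With a site difference of .3 to .8 SD, the bias in B2 is about −.015 to −.04 SD as written and at most about −.006 SD with the × Time terms. With dropout unrelated to site and arm, mean B2 was .497 to .502 against a true .5.

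**The case against.** The case for leaving the model alone is fair, and most of it stands.

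- A reader might infer that the plan claims its model equals an ANCOVA adjusted for gender and site. It does not. It says similar and analogous, and ties the analogy to control for baseline QOL through the equal-baseline constraint. That claim is sound.
- Gender and site are not inert. They enter the follow-up comparison with the factor (1 − β).
- A reader might infer that precision is necessarily lost. It is lost only if gender or site effects change over time. At small differences there is no measurable gain from the interactions.
- Nothing in the documents establishes a large site difference. Other recruitment routes are listed beside the teaching visit, and eligibility sets no limit on time since diagnosis for youth, so those two sites can enrol a mix. A site difference of .5 SD would equal the whole effect the trial is powered for.
- The dropout case is constructed. Its worst bias is about .04/.13 = .3 of a standard error.
- The power statement rests on an unadjusted t-test and is untouched.

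What this does not answer is the mismatch itself. The plan names gender and site as covariates for a comparison of change, fixes their effect on change at zero, and gives no reason to expect stable effects.

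**Conclusion.** The point holds as a minor one. The written model adjusts for gender and site only partly, under an unstated restriction that their effects are the same at baseline and post-intervention. Under simple randomization and ρ = .6, the cost in the SD of B2 is about nil for site differences in change up to .3 SD, 2–3% at .5 SD and 8–10% at .8 SD. It is smaller in true spread if arms are balanced within site. With dropout that also differs by site and arm, a bias of about .015–.04 SD is possible.

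These sizes rest on assumed values of ρ, D, site sizes and dropout pattern, and on an unstructured covariance. A reader might conclude that the trial is underpowered or that its primary estimate is biased in general. The documents support neither: 94% and 88% stand, and B2 is unbiased under randomization apart from the specific dropout pattern described.

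**What to change.** In Methods 2.0, add Time × Gender and Time × Site to the primary model, with site as a four-level class variable. State an unstructured covariance for the two time points. Keep the equal-baseline constraint and keep B2 as the treatment effect. Carry the same terms to the secondary between-arm models; the time-only model for mentors needs no change. If the sponsor prefers the model as written, the plan should say that constant gender and site effects are intended, and why.

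The cost is SAP wording, one line of code and four parameters (one for gender, three for site) in 200 youth. If gender and site effects are in fact stable over time, the SD of B2 rises by about 1%.

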Optimal self-management of a chronic illness includes managing its effects on life as well as medical self-management. Yet self-management interventions typically focus only on medical management. This is a problem because up to 35% of youth with IBD experience clinically significant difficulty in other areas of self-management, particularly in managing the overall impact of the disease on life (e.g., quality of life), even when the disease is inactive. The objective of this study is to address areas of impairment that persist even during remission with a multifaceted peer mentoring program. Mentoring programs are common in the general population and are well-known to improve a plethora of outcomes, including social, emotional and academic outcomes, all of which are necessary for successfully managing life with IBD. Peer mentoring programs in particular offer innovative advantages over other forms of intervention for youth with IBD: 1) A peer mentor is a role model who normalizes and de-stigmatizes the disease in a way that a professional cannot, and 2) With a peer mentor, self-management activities take place within the community, promoting generalization and independence in ways that traditional interventions do not. Our mentoring program was developed via focus groups, an NIH-funded pilot study, national mentoring resources, and the PI's 10 years of experience with Big Brothers Big Sisters. It consists of year-long, 1:1 mentee-mentor relationships with group self-management activities, a private program website, and a parent support component. Our pilot study demonstrated feasibility, satisfaction, and improvement in the areas of quality of life (QOL), functioning in typical life activities, IBD self-efficacy, and rates of remission. In the proposed study, 200 youth and their parents, and 100 mentors will be enrolled in this multisite, randomized controlled clinical trial comparing those in the Mentoring Program to an Educational Activity comparison group in the areas of QOL, functioning in typical life activities, and disease outcomes (e.g., biomarker and standardized indices). Mechanisms that contribute to outcomes, including perceived stigma, disease-related self-efficacy, coping and disease uncertainty will be examined as well.

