## Study Summary

**Make Sure You Click the [Save Link](#) (Above) Frequently While Entering Your Information.**

- 1.0 \* Describe the background and rationale for this project. Reference to peer reviewed literature is desirable:**

Inflammatory bowel disease (IBD; Crohn's disease and ulcerative colitis) affects over 1 million people in the US. Unpredictable symptoms of abdominal pain, frequent diarrhea and fatigue can present significant challenges to living well with this chronic disease. Symptoms can be embarrassing and can result in spending a great deal of time in the bathroom. Youth with IBD can be reluctant to talk about their symptoms with peers, embarrassed by their frequent visits to the bathroom, and fearful of becoming the target of the "bathroom humor" popular among youth. In

fact, 84% of individuals with IBD report feeling disease-related stigma.

IBD results in significantly impaired QOL and functioning in typical life activities. Our early work found that youth with IBD had significantly worse social functioning than healthy children, reaching clinical significance in over a third. A meta-analysis provided further support for significant social difficulty, as well as impaired QOL. We also found that youth with IBD had significantly more school absences than healthy children.

The impaired QOL and life functioning occur with mild and remitted disease, highlighting the importance of targeting management of these nonmedical areas. In our studies investigating social functioning and school absences, 94% of the children with IBD had mild symptoms or were in remission, suggesting difficulties persist even when the disease is not particularly active. In the school absence study, psychosocial factors were significant predictors of absences, but disease factors were not, suggesting that interventions focusing on medical management may be of limited utility in promoting functional abilities.

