## 4.0 If this research is hypothesis driven, succinctly state the hypothesis:

Hypothesis 1a: Participants in the Mentoring Program will have significantly improved QOL compared to those in the Educational Activity group post-intervention and 6 months later.

Hypothesis 1b: Participants in the Mentoring Program will have significantly improved functioning in typical life activities (i.e., functional abilities) and better disease outcomes (e.g., less severe disease as measured via biomarker and standardized indices) post-intervention and 6 months later.

Hypothesis 2a: Parents in the Mentoring Program will have significantly improved QOL compared to those in the Educational Activity group post-intervention and 6 months later.

Hypothesis 2b: The QOL of the mentors will significantly improve from baseline to post-intervention.

Hypothesis 3: Parent and child self-efficacy, illness uncertainty, coping, social support and child perceived stigma will mediate relationships between mentoring and outcomes. Sex will be explored as a moderator.

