Follow-up assessments will occur post-intervention and 6 months post-intervention. School absences will be obtained from each child's school at the baseline and post-intervention assessments. Chart reviews will be conducted for disease and outcome information including number of relapses, number of hospitalizations, number of days hospitalized, number of procedures, number of clinic appointments scheduled, and clinic attendance ratio (number of appointments attended/number scheduled). Medications will also be recorded. Disease severity will be assessed via standardized measures of disease activity (Pediatric Crohn's Disease Activity Index or the Pediatric Ulcerative Colitis Activity Index), physician global assessment (PGA; overall assessment of current disease severity based physical examination and patient report, categorized into remission, mild, moderate or severe disease activity), and the biomarker of fecal calprotectin, a commonly used biomarker in IBD.

Stool will be collected at baseline and post-intervention for the fecal calprotectin, which will be analyzed at CCHMC by site co-I [name]. A stool collection kit will be mailed to participants prior to the study visit, with instructions to collect the stool sample within 24 hours of the upcoming visit. A reminder phone call will be made the day before. Research staff will transport the sample back to the hospital and send it to CCHMC.

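### Must the plan fix a scale for calprotectin and a rule for joining PCDAI and PUCAI before the Hypothesis 1b disease tests can stand?

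*Combined protocol and SAP*

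**What the plan says.** Hypothesis 1b (Study Summary 4.0) covers functional abilities and disease outcomes, the latter described as "less severe disease as measured via biomarker and standardized indices". Methods 1.0, under Procedures, names the measures: the Pediatric Crohn's Disease Activity Index (PCDAI) "or the Pediatric Ulcerative Colitis Activity Index" (PUCAI), a four-category physician global assessment, and "the biomarker of fecal calprotectin, a commonly used biomarker in IBD".

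Methods 2.0 sets out one linear repeated-measures model for youth quality of life (QOL). The treatment effect is the coefficient B2 on Time x Treatment. The section adds that "only the pre-specified covariates of baseline outcome variable, gender, and site will be included in the primary and secondary analyses". For the secondary hypotheses it states "The same approach and statistical models employed for our primary hypotheses will be used for our secondary hypotheses", and continues: "The main difference between the precise models used will be (a) the specific outcome variable", with the time point as the second difference.

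Nothing in the document says whether the two indices are analysed separately or on a common scale. Nothing gives a transformation or an assay-limit rule for calprotectin.

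**The concern.** Any IBD diagnosis is eligible, so both indices will be in use. Suppose disease activity is taken as a single outcome and put into the stated model as it stands. Some children then contribute PCDAI points and others PUCAI points, with no diagnosis term, and B2 averages two units with no readable size. Calprotectin goes into the same linear model on whatever scale the laboratory reports. If its distribution is skewed, a few large values could dominate the comparison and cost power.

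At stake are the trial's tests of disease outcome. If the analysis were chosen after the data were seen, the nominal 5% error rate of those tests would also be in doubt.

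**Working it through.** **1. The plan's own power figure.** Inputs from Sample Size Information 2.0: alpha 0.05, d = 0.5, 100 per arm, or 80 after 20% attrition. Power = Φ(d√(n/2) − 1.96).
- n = 100: 0.5 × √50 = 3.536; Φ(1.576) = 94.2%, stated 94%.
- n = 80: 0.5 × √40 = 3.162; Φ(1.202) = 88.5%, stated 88% (a noncentral t gives 88.2%).

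Both reproduce. They concern QOL only; no power is claimed for disease outcomes.

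**2. Does the text mix the indices?** Hypothesis 1b speaks of indices in the plural. Methods 1.0 names two instruments, one or the other per child. Methods 2.0 lets the outcome variable change from model to model. One model for PCDAI and one for PUCAI therefore follows the text at least as closely as a pooled model, and it needs no extra covariate. The global assessment also gives a severity rating that does not depend on diagnosis, although no model is stated for it.

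**3. Calprotectin scale.** All inputs are assumed: log-normal values, baseline-to-post correlation 0.4 on the log scale, 80 per arm, 10,000 trials per cell. The analysis was ANCOVA, whose treatment estimate with complete data equals B2 in the stated model. Power, untransformed / log (%):

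| Effect | log-SD 0.5 | 1.0 | 1.6 |
|---|---|---|---|
| Ratio 0.6 in every child | 100 / 100 | 76 / 94 | 24 / 59 |
| Ratio 0.8 in every child | 80 / 86 | 21 / 33 | 7 / 16 |
| Halved if baseline above median | 98 / 99 | 54 / 64 | 18 / 31 |
| Halved if baseline in top quarter | 55 / 60 | 20 / 21 | 8 / 12 |
| Halved if post value above median | 100 / 100 | 85 / 76 | 34 / 36 |
| Halved if post value in top quarter | 95 / 77 | 58 / 26 | 24 / 12 |
| Capped at 75th percentile | 45 / 20 | 69 / 20 | 74 / 20 |

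The better scale depends on how the intervention acts. The documents give neither a mechanism nor a distribution.

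**4. Indices.** Assumed: 50:50 diagnosis split, within-index correlation 0.5, 80 per arm, 4,000-6,000 trials per cell. Power, raw pooled / standardised within index (%):

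| Effect | SD ratio 1.25 | SD ratio 2 |
|---|---|---|
| 0.4 SD in both diseases | 82 / 82 | 77 / 82 |
| 0.6 SD, narrower index only | 46 / 56 | 27 / 57 |
| 0.6 SD, wider index only | 64 / 57 | 75 / 58 |

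With equal effects and SD ratio k, the wider index supplies k/(1+k) of a raw pooled contrast: 1.25/2.25 = 56%, or 2/3 = 67%. That hurts interpretation but costs little power.

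Separate models give readable units at a price. Take an assumed 70:30 split (56 and 24 per arm), an effect of 0.4 SD and SE = √(2/n × 0.75):
- n = 56: SE 0.164, Φ(2.44 − 1.96) = 69%.
- n = 24: SE 0.250, Φ(1.60 − 1.96) = 36%.
- All 80 on one scale: SE 0.137, Φ(2.92 − 1.96) = 83%.

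**5. Type I error.** For one calprotectin analysis fixed in advance, over log-SD 0.5 to 2.0, simulated error was 2.8-5.1% untransformed and 4.9-5.2% on the log scale. For one index analysis fixed in advance it was 4.3-5.8%. If the more favourable of raw and log were always reported, it would be about 7-8%. For the best of four index analyses (pooled raw, standardised, each index alone) it would be about 11-12%.

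**The case for a change.** The strongest case is that the silence is real and the remedy short. Two statisticians could both follow Methods 2.0, test different index hypotheses on different numbers of children, and both claim compliance. The tables show that the choice can decide whether an effect is detected. Left open until results are visible, it also permits the 7-8% and 11-12% error rates above. Nor can a narrow spread be taken for granted: there is no disease-activity criterion for entry, and two sites approach newly diagnosed patients.

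Part of this stands. The plan is not explicit, and a raw pooled index contrast would be hard to interpret if anyone fitted one. But the inflated rates describe selective reporting, which the plan does not invite. The case also does not show that a particular remedy improves on the plan. Evidence on spread runs the other way too: in two earlier studies by the investigators "94% of the children with IBD had mild symptoms or were in remission", and the trial means to "address areas of impairment that persist even during remission". In such a sample an effect confined to the high post-intervention values is plausible, and there the log scale loses. A diagnosis term added after within-index standardisation moved power by less than one percentage point in simulation (for example 82.5% to 82.3%, and 56.3% to 56.9%). That is a thin reason to break the plan's covariate rule.

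**Conclusion.** No change to the plan follows. This is missing detail on secondary outcomes that a competent analyst fills sensibly: one model per index, and one calprotectin scale settled before results are seen by arm. The text already accommodates both. The charge that the model mixes index units rests on a reading that the plan does not require.

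On calprotectin, the untransformed analysis that the model gives as written is a valid test, with simulated type I error of at most 5.1%. Its power relative to the log scale ranges, at log-SD 1.0, from 18 points worse (76% against 94%) to 49 points better (69% against 20%), depending on an unknown mechanism. On the indices, standardising gains 0 to 5 points with equal effects, and gains or loses otherwise.

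All these comparisons rest on assumed distributions, correlations, case mix and effects, since the documents supply none. The primary QOL analysis and its 94% and 88% power figures are unaffected.
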